### Table 1Study Phases

A subject who adheres to the study treatment and assessment schedule (as detailed in Time and Events Table, Section 7.1) will be considered to have completed the study if they complete all of the assessments at the End of Study visit (Visit 5). A subject who permanently discontinues study treatment early will be withdrawn from the study after completing the Early Withdrawal visit (See Time and Events Table, Section 7.1).

Subjects receiving mepolizumab prior to the study will be advised to continue with their pre-study mepolizumab treatment following completion of the assessments at the End of Study/Early Withdrawal visit. Subjects not receiving mepolizumab prior to the start of the study will have mepolizumab treatment stopped at the End of Study/Early Withdrawal visit and will receive appropriate care and treatment as determined by their treating physician.

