## Liver Chemistry Increased Monitoring Algorithm with Continued Therapy for ALT ≥3xULN but <8xULN

\*INR value not applicable to subjects on anticoagulants

Required actions and follow-up assessment for all subjects who meet liver chemistry stopping or monitoring criteria are defined in Appendix 4.

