### 5.5.2.1. Study Treatment Restart or Rechallenge

Study treatment restart or rechallenge after liver chemistry stopping criteria are met, by any subject participating in this study, is not allowed.

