## 6. STUDY TREATMENT

## 6.1. Investigational Product and Other Study Treatment

The term 'study treatment' is used throughout the protocol to describe the mepolizumab drug product in autoinjector received by the subject as per the protocol design.

Mepolizumab liquid drug product will be supplied by GSK in Type I glass syringes with staked needles (1/2 inch x 29 gauge thin wall), sealed with latex-free rubber plungers. These will be assembled in single use, disposable autoinjectors to enable automatic delivery of the drug product. Each device will deliver 100mg mepolizumab in 1.0mL. The formulation contains sodium phosphate, citric acid, sucrose, EDTA and polysorbate 80.

	Study Treatment
Product name:	Mepolizumab (NUCALA) (SB240563)
Device:	Prefilled syringe contained within an autoinjector
Formulation description:	100 mg/mL mepolizumab with sodium phosphate, citric acid,
	sucrose EDTA and polysorbate 80
Dosage form:	Sterile, liquid formulation
Unit dose	100 mg/mL; 1.0mL (deliverable)
strength(s)/Dosage level(s):	
Route of Administration	SC injection
Dosing instructions:	SC dose in thigh, abdomen or upper arm every 4 weeks
Physical description:	Clear to opalescent, colourless to pale yellow sterile solution for
mepolizumab	SC injection in a single-use, prefilled syringe contained within an
	autoinjector
Physical description of	Single use, disposable autoinjector assembled with the prefilled
injection device:	syringe containing the drug product. The autoinjector enables
	automatic delivery of the drug product under the power of a
	spring mechanism following activation of the device. Start and
	end of injection clicks inform the user of correct use. A plastic
	needle cover shields the needle before and after injection to
	minimise the potential for needle stick injuries.
Manufacturer/source of	Prefilled syringe: Prefilled syringe components are procured
procurement:	from Becton Dickinson. Prefilled syringe is filled with drug
	product and assembled at GSK, Barnard Castle, UK.
	Autoinjector: The autoinjector components are manufactured by
	Ypsomed AG and assembled with the prefilled svringe at GSK
	Barnard Castle, UK.

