- c. Parasitic screening is only required in countries with high-risk or for subjects who have visited high-risk countries in the past 6 months. Sites should use local laboratories.
- d. Perform prior to mepolizumab administration during the study and prior to restarting pre-study mepolizumab treatment on study completion/early withdrawal.
- e. Subjects will be instructed to contact clinical study staff at any time if they have concerns or questions regarding self-administration. They will have the option of returning to the clinical site for further training or assistance with self-administration. Requirement for additional training or assistance will be documented.
- f. Self-administration of mepolizumab using the autoinjector should occur within 24 hours following the clinic visit.
- g. Includes measurement of eosinophil levels for pharmacodynamic analysis at Visits 2, 3, 4 and 5
- h. Pharmacogenetic sample may be drawn any time after the respective informed consent form is signed and the subject is enrolled.
- i. Vital signs include temperature, sitting blood pressure, respiratory rate and pulse.
- j. Any SAEs assessed as related to study participation (e.g., study treatment, protocol-mandated procedures, invasive tests, or change in existing therapy) or related to a GSK concomitant medication, will be recorded from the time a subject consents to participate in the study up to and including any follow up contact. All other AEs/SAEs are recorded from the start of study treatment until the End of Study / Early Withdrawal visit.
- k. Injection site reactions (e.g., induration, erythema, edema, rash, pruritus, pain) are to be recorded on both AE and SAE CRF forms.
- I. Information on systemic reactions and events that meet the anaphylaxis criteria is collected on both AE and SAECRF forms
- m. Patient diary should be dispensed prior to administration of injection
- n. For any subject who withdraws prior to Week 12, patient diary and study drug for self-administration outside of clinic will be returned at the Early Withdrawal visit (if applicable).

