# 12.4. Appendix 4: Liver Safety Required Actions and Follow up Assessments

# 12.4.1. Liver chemistry stopping criteria and required follow up assessments

	Liver Chemistry Stopping Criteria - Liver Stopping Event				
ALT-absolute	$ALT \ge 8xULN$				
ALT Increase	ALT $\ge$ 5xULN but <8xULN persists for $\ge$ 2 weeks ALT $\ge$ 3xULN but <5xULN persists for $\ge$ 4 weeks				
Bilirubin 	ALT $\ge$ 3xULN and bilirubin $\ge$ 2xULN (>35% direct bilirubin)				
INR 	ALT $\geq$ 3xULN and INR>1.5, if INR measured				
Cannot Monitor	ALT $\ge$ 5xULN but <8xULN and cannot be monitored weekly for $\ge$ 2 weeks ALT $\ge$ 3xULN but <5xULN and cannot be monitored weekly for $\ge$ 4 weeks				
Symptomatic 	ALT $\geq$ 3xULN associated with symptoms (new or worsening) believed to be related to liver injury or hypersensitivity				
Required Actions and Follow up Assessments following ANY Liver Stopping Event					

	Actions		Follow Up Assessments
•	Immediately discontinue study treatment	•	Viral hepatitis serology 
•	Report the event to GSK within 24 hours	•	Only in those with underlying chronic
•	Complete the liver event CRF and complete an SAE data collection tool if the event also meets the criteria for an SAE 		hepatitis B at study entry (identified by positive hepatitis B surface antigen) quantitative hepatitis B DNA and hepatitis delta antibody  .
•	Perform liver event follow up assessments	•	Blood sample for pharmacokinetic (PK)
•	Monitor the subject until liver chemistries resolve , stabilize, or return to within baseline		analysis, obtained within 4 weeks after last dose 
•	(see MONITORING below) Do not restart/rechallenge subject with	•	Serum creatine phosphokinase (CPK) and lactate dehydrogenase (LDH).
	study treatment. Permanently discontinue study treatment and may continue subject in the study for any protocol specified follow up	•	Fractionate bilirubin, if total bilirubin≥2xULN
	assessments	•	Obtain complete blood count with differential to assess eosinophilia. Note: the mechanism of action of mepolizumab leads to lowering of eosinophils.

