MO For	NITORING: bilirubin or INR criteria: Repeat liver chemistries (include ALT, AST, alkaline phosphatase, bilirubin) and perform liver event follow up assessments within 24 hrs	•	Record the appearance or worsening of clinical symptoms of liver injury, or hypersensitivity, on the AE report form Record use of concomitant medications on the concomitant medications report form including acetaminophen, herbal remedies, other over the counter medications.
•	Monitor subjects twice weekly until liver chemistries resolve, stabilize or return to within baseline	•	Record alcohol use on the liver event alcohol intake case report form
•	A specialist or hepatology consultation is recommended	Foi	r bilirubin or INR criteria:
•	All other criteria: Repeat liver chemistries (include ALT, AST, alkaline phosphatase, bilirubin) and perform liver event follow up assessments within 24- 72 hrs Monitor subjects weekly until liver chemistries resolve, stabilize or return to within baseline	•	Anti-nuclear antibody, anti-smooth muscle antibody, Type 1 anti-liver kidney microsomal antibodies, and quantitative total immunoglobulin G (IgG or gamma globulins). Serum acetaminophen adduct HPLC assay (quantifies potential acetaminophen contribution to liver injury in subjects with definite or likely acetaminophen use in the preceding week [James, 2009]). NOTE: not required in China
		•	Liver imaging (ultrasound, magnetic resonance, or computerised tomography) and /or liver biopsy to evaluate liver disease  complete Liver Imaging and/or Liver Biopsy CRF forms.

- Serum bilirubin fractionation should be performed if testing is available. If serum bilirubin fractionation is not immediately available, discontinue study treatment for that subject if ALT ≥ 3xULN and bilirubin ≥ 2xULN. Additionally, if serum bilirubin fractionation testing is unavailable, record presence of detectable urinary bilirubin on dipstick, indicating direct bilirubin elevations and suggesting liver injury.
- All events of ALT ≥ 3xULN and bilirubin ≥ 2xULN (>35% direct bilirubin) or ALT ≥ 3xULN and INR>1.5, if INR
  measured which may indicate severe liver injury (possible 'Hy's Law'), must be reported as an SAE (excluding
  studies of hepatic impairment or cirrhosis); INR measurement is not required and the threshold value stated
  will not apply to subjects receiving anticoagulants

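### Protocol Section 4.2 advises all prior mepolizumab users to continue it after the last visit, with no exception for subjects who met liver stopping criteria

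*Protocol*

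**What the plan says.** Section 4.2 sets out what happens after the End of Study/Early Withdrawal visit. For prior users: "Subjects receiving mepolizumab prior to the study will be advised to continue with their pre-study mepolizumab treatment following completion of the assessments". The next sentence, on subjects not previously treated, stops mepolizumab and leaves further care to the treating physician. The sentence on prior users has no such clause.

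Footnote d of the Time and Events Table (Section 7.1), attached to the blood samples among other procedures, makes the same assumption: "Perform prior to mepolizumab administration during the study and prior to restarting pre-study mepolizumab treatment on study completion/early withdrawal".

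The liver rules are these:

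- Section 5.5.1 withdraws a subject who meets any liver stopping criterion, in consultation with the medical monitor and principal investigator.
- Section 5.5.2.1: "Study treatment restart or rechallenge after liver chemistry stopping criteria are met, by any subject participating in this study, is not allowed".
- Appendix 4 (12.4.1) repeats the bar and adds: "Permanently discontinue study treatment and may continue subject in the study for any protocol specified follow up" assessments.
- Section 6.1 fixes the key term: "The term 'study treatment' is used throughout the protocol to describe the mepolizumab drug product in autoinjector received by the subject".

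The SAP plans summaries of any liver stopping or monitoring events (Section 11.2) but says nothing about treatment after the study.

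**The concern.** A rule against rechallenge after a liver stopping event exists to avoid re-exposing the subject to a drug that may have caused it. Here the rule attaches to a presentation, the autoinjector, while the advice in Section 4.2 concerns the same active substance in whatever form the subject used before the study. A subject can be permanently barred from the one and, on the written text, advised to go back to the other.

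The stake is individual patient safety: a further dose advised while liver chemistry is still abnormal. It does not touch the primary endpoint, the analysis populations or the sample size.

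**Working it through.** No arithmetic applies. The check follows one subject through the text.

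1. **Who.** A subject enters under inclusion criterion 3b, on 100 mg SC mepolizumab every 4 weeks for at least 12 weeks before Visit 1, and meets an Appendix 4 stopping criterion during the study.
2. **Withdrawal.** Sections 5.5 and 5.5.1 take the subject off study treatment and out of the study, with an Early Withdrawal visit 4 weeks (±7 days, footnote b) after the last dose. If the criterion is met after the third and last dose at Week 8, the corresponding final visit is Visit 5. Section 4.2 names both visits, so its advice reaches the subject either way. With dosing every 4 weeks, the visit falls at about the time the next dose would be due.
3. **Does the restart bar reach the pre-study product?** Section 5.5.2.1 and Appendix 4 both speak of study treatment. By the Section 6.1 definition, which applies throughout the protocol, that is the autoinjector product given under this protocol. Mepolizumab prescribed outside the study is not included.
4. **Is the pre-study product different enough to justify different handling?** The protocol treats the two as equivalent. Section 2.1 reports that comparability between the liquid and lyophilised products was demonstrated. Section 4.5 matches the dose to the marketed form, and Section 4.6 expects a similar safety profile. Criterion 3b gives the same dose and interval.
5. **Does any other text make resumption depend on the liver outcome?** The candidates are:
   - *Section 5.5.2*: "Required actions and follow-up assessment for all subjects who meet liver chemistry stopping or monitoring criteria are defined in Appendix 4". Appendix 4 therefore continues to govern the subject's liver follow-up.
   - *Appendix 4 (12.4.1)*: reporting to the sponsor within 24 hours. Follow-up assessments are due within 24 hours for the bilirubin or INR criteria and within 24 to 72 hours otherwise. Monitoring is twice weekly for the bilirubin or INR criteria; for the others, "Monitor subjects weekly until liver chemistries resolve, stabilize or return to within baseline".
   - *Appendix 4 (12.4.2)*: for ALT of 3 to <8xULN with bilirubin <2xULN and no symptoms, the medical monitor is notified within 24 hours and chemistries are repeated weekly, before any stopping criterion is met.
   - *Notes to Table 3 (Section 7.7.7)*: clinically significant abnormal values are repeated, and if they do not normalise the cause is sought and the sponsor told.
   - *Footnote d*: chemistry is drawn before restart. It does not say that the result must be seen first.
   - *Section 6.10*: the investigator must see that post-study care is considered.

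   Each of these requires monitoring, work-up, notification or general consideration. None says that the Section 4.2 advice is withheld, or that resumption waits for the liver event to settle.

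**The case against.** The strongest reply is that Section 4.2 is general post-study advice, not a dosing instruction. The sponsor plans no supply after the study, the patient already had a treating physician and a prescription, and Section 6.10 puts post-study care on the investigator. By the final visit a subject with a stopping event will usually have had medical monitor involvement, serial liver tests and a work-up begun. Few investigators would read a generic sentence as overriding that. The Section 4.6.1 risk table lists no hepatic risk, and entry requires ALT no higher than 2xULN (Section 5.3). All of this stands and keeps the point small. It does not supply the missing exception: the specific sentence still points towards continuing.

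A second reply is that the same sentence also covers subjects withdrawn for QTc, other laboratory changes or pregnancy, so singling out the liver is arbitrary. The observation is correct. The liver case differs because it is the one for which the protocol writes an explicit ban on rechallenge, which the post-study advice then bypasses.

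Three stronger readings are tempting but not supported:

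- **That the protocol contradicts itself.** It does not. The bar and the advice apply to different products as defined, and Section 5.5.2 keeps Appendix 4 in force for every subject who meets the criteria.
- **That the cause will be unassessed at the visit.** Appendix 4 starts the work-up within 24 to 72 hours at most, and Appendix 6 requires a causality judgement for each AE or SAE. The work-up may be incomplete, but the documents do not support saying that it will not have been done.
- **That the advice should also be withheld while a persistence criterion is still being judged.** Section 12.4.2 lets such subjects continue study treatment under weekly monitoring. A stricter rule for post-study mepolizumab would be inconsistent with that.

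**Conclusion.** The gap is real and minor. As written, Section 4.2 and footnote d allow a subject who met liver stopping criteria to be advised back onto the same drug and dose before the event has resolved, because the restart bar is confined to the autoinjector product. Several safeguards make this unlikely, but none ties resumption to the liver outcome.

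The size cannot be given as a rate. The documents report neither the expected number of criterion 3b subjects nor the frequency of liver stopping events, and visit timing alone says nothing about how often harm would follow. A reader might infer a hepatic safety signal or a dose imposed by the study; the documents show neither.

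The conclusion assumes that the Section 6.1 definition is applied literally. It also assumes that the liver algorithms in Section 5.5.2, which are figures not available in the text reviewed, contain no exception for pre-study mepolizumab. It should be treated as a safety wording correction.

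**What to change.** Add one sentence to Section 4.2 and a cross-reference to it in footnote d of Section 7.1. Suggested wording:

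*Subjects who met liver chemistry stopping criteria will not routinely be advised to continue pre-study mepolizumab at the End of Study/Early Withdrawal visit. Resumption will be decided by the treating physician, in discussion with the medical monitor, once Appendix 4 monitoring shows that liver chemistries have resolved, are stable or are back at baseline, and the cause has been assessed.*

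This does not prohibit resumption, and it leaves subjects under Section 12.4.2 monitoring who have not met a stopping criterion as they are. Section 5.5.2.1, the Appendix 4 rechallenge bar and the SAP need no change.

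The cost is the one sentence and the cross-reference. The clinical downside is a possible gap in mepolizumab for the few subjects affected, with asthma control managed by the treating physician in the meantime.

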## 4.3. Type and Number of Subjects

Approximately 225 subjects with severe eosinophilic asthma will be screened in order to achieve 158 enrolled subjects (attempting at least one self-administration of mepolizumab) and 150 subjects with complete study data. Approximately 100 subjects will use autoinjectors with labelling that includes a pictogram plus standard labelling elements and 50 subjects will use the standard labelling without the pictogram.

## 4.4. Design Justification

An open-label, repeat-dose, single arm, multi-centre study design is deemed appropriate to evaluate self-administration of mepolizumab liquid drug product in autoinjector in subjects with severe eosinophilic asthma. The primary purpose, and resultant study design is to assess the appropriate use of the autoinjector in a real world use setting. Participants are intended to be broadly representative of patients and caregivers (i.e., similar age, dexterity and cognitive abilities, degree of training or experience with an autoinjector) who may use the autoinjector, either for the treatment of severe eosinophilic asthma or, potentially, other approved indications. In addition, safety outcomes, immunogenicity, pharmacokinetics and pharmacodynamics will be also be characterised in this study.

A population of subjects with severe eosinophilic asthma either currently receiving or not currently receiving commercially available mepolizumab SC at study entry (Visit 1) was selected to reflect the intended population in "real world" use conditions. Subjects not currently receiving mepolizumab will have a history of  $\geq 1$  exacerbations requiring treatment with systemic corticosteroids in the previous 12 months while using, or having a requirement for, high dose inhaled corticosteroids (ICS) plus a second controller.

Due to differences in the labelling requirements among regulatory authorities around the world, two different labelling approaches will be included in this global study: labelling that includes a pictogram plus standard labelling elements, or a standard labelling without the pictogram. The pictogram plus standard labelling elements is intended to satisfy requirements of the US Food and Drug Administration; while the standard labelling (without pictogram) is intended to satisfy requirements of Regulatory Agencies outside of the United States. English speaking subjects outside of the US can contribute to the cohort used to assess the US label. All subjects at a given clinical trial site will utilise the same format of device label for all injections throughout the study. The assessment of injection success will be reported separately according to the format of labelling used.

The standardised training provided in this study will be representative of the instruction and training materials that will be given once the device is commercially available for use. Subjects will be observed self-administering liquid drug product from the autoinjector immediately after being trained in its use at Visit 2 (Week 0). Subjects will self-administer at 4-weekly intervals, either at the clinic or outside of the clinic (Time and Events Table, Section 7.1). The primary endpoint of the study will be assessed under observation at Visit 4, 8 weeks after the subject received training in the use of the autoinjector.

With regards to the pharmacokinetic and pharmacodynamic assessments, it is acknowledged that mepolizumab exposure will not be at steady-state after the first and second SC doses (administered at Visits 2 and at home following Visit 3, respectively) in those subjects not previously receiving mepolizumab treatment at Visit 1; however, mepolizumab plasma concentration at the end of the dosing interval (Ctrough) measurements can be compared with historical data. Likewise data from the Phase III study MEA115588 showed that in subjects previously not treated with mepolizumab, the reduction in blood eosinophil count at the end of the dosing interval following the first SC dose of mepolizumab (i.e. pre-steady-state) was close to the reduction observed at the end of the dosing interval following the eighth SC dose of mepolizumab (i.e. at steadystate). Therefore, in those subjects not receiving mepolizumab treatment at Visit 1, assessing the pharmacodynamic effect of mepolizumab is still of interest.

## 4.5. Dose Justification

The 100 mg dose of mepolizumab liquid drug product in autoinjector will match the dose of reconstituted lyophilised drug product (the currently marketed form).

